**Table 5. PTC Therapeutics Serious Adverse Event Regulatory Reporting Requirements**

Type of Event			Type of Report	Timeframe for Reporting To Health Authorities
Fatal or Life-Threatening	Unexpected	Related		
Yes	Yes	Yes	Telephone/Fax notification or report	Within 7 calendar days of PTCAD or according to local regulations
			FDA Form 3500A or CIOMS I form	Within 15 calendar days of PTCAD or according to local regulations
No	Yes	Yes	FDA Form 3500A or CIOMS I form	Within 15 calendar days of PTCAD or according to local regulations
Yes	No	Yes	Annual report	Annually
No	No	Yes		
Yes	Yes	No		
No	Yes	No		
Yes	No	No		
No	No	No		

a. Includes possibly or probably related events

Abbreviations: CIOMS I = Council for International Organizations of Medical Sciences, FDA = Food and Drug Administration, PTCAD = PTC Therapeutics Awareness Date

If notification of an adverse event requiring expedited reporting is received, PTC Therapeutics will contact each investigator using PTC299 by e-mail or regular mail within 15 working days from the PTCAD such that the Investigator can promptly notify the site IRB. A complete written report will follow the initial notification. PTC will receive all SAE notifications via AdeERS. Although AdeERS reports are automatically forwarded to the FDA, PTC will maintain responsibility for ensuring all events are reported to the FDA according to federal requirements according to the Regulatory Reporting Requirements listed in Table 5 above. Routine reporting of all AEs will be recorded by the sites on the Adverse Event Form CRF.

## **7.0 CRITERIA FOR DISCONTINUATION**

- Study medication will be interrupted or permanently discontinued for treatment related toxicities as outlined in Section 5.3.3.
- Disease progression.
- Subjects who show no more than stable disease after six 4-week cycles of treatment will be permanently removed from treatment.
- Subjects who show a partial response will be treated for up to twelve 4-week cycles.
- Subjects who show a complete response will be treated for two 4-week cycles beyond confirmation of complete response.
- Subjects who become pregnant or breast-feed or who require systemic chemotherapy for the treatment of a malignancy other than KS.
- Subjects who require treatment with medications which are disallowed as outlined in Section 5.4.2.
- Subjects who are noncompliant with respect to taking drugs, keeping appointments or having tests required for the evaluation of drug safety and efficacy.
- Subjects have the right to withdraw from the study at any time for any reason.
- The Investigator has the right to remove subjects from the study for clinical reasons which he/she believes are life threatening to the subject even if such reasons do not fall into the toxicity classifications discussed above.

## 8.0 EVALUATION OF RESPONSE

All subjects will be evaluated for response by physical examination and by relevant imaging studies at Day 29 and every 28 days thereafter ( $\pm 7$  days).

### 8.1 Definition of Response

8.1.1 Complete response (CR) is defined as the absence of any detectable residual disease, including tumor-associated edema, persisting for at least 4 weeks. In subjects in whose pigmented (brown or tan) macular skin lesions persist after apparent CR, biopsy of at least one representative lesion is required in order to document the absence of malignant cells. In subjects known to have had visceral disease, an assessment at restaging with appropriate endoscopic or radiographic procedures should be made.

8.1.2 Partial response (PR) is defined as no new lesions (skin or oral), or new visceral sites of involvement (or the appearance or worsening of tumor-associated edema or effusions); AND

- A 50% or greater decrease in the number of all previously existing lesions lasting for at least 4 weeks; OR
- Complete flattening of at least 50% of all previously raised lesions (i.e., 50% of all previously nodular or plaque-like lesion become macules); OR
- A 50% decrease in the sum of the products of the largest perpendicular diameters of the marker lesions

Note: Subjects with residual tumor-associated edema or effusion who otherwise meet the criteria for CR will be classified as having a PR.

8.1.3 Stable disease is defined as any response not meeting the criteria for CR, PR, or progressive disease.

8.1.4 Progressive disease (PD) is defined as follows:

For subjects with <50 cutaneous lesions:

- $\geq 25\%$  increase in the sum of perpendicular diameters of the indicator lesions; OR
- $\geq 25\%$  increase in the total lesion count, or a minimum of 5 new lesions, whichever is greater; OR
- $\geq 25\%$  increase in the number of raised lesions (minimum of 5 new raised lesions if there are very few raised lesions, for example  $\leq 8$ ), whichever is greater.

Note: There are body sites where disease is particularly difficult to evaluate, and a few new lesions may be counted in spite of the fact that a subject is not actually progressing. For example, lesions of the foot, particularly those which are flat, are difficult to evaluate because their intensity may be variable based on how much edema is present, how much the person walked the day before, how long their feet have been in a dependent position prior to the physical exam, etc.

For subjects with >50 cutaneous lesions:

- $\geq 25\%$  increase in the sum of the perpendicular diameters of the indicator lesions; OR

- $\geq 25\%$  increase in the total number of lesions in the prospectively defined anatomic sites containing representative numbers of lesions; OR
- A total of 5 new lesions in anatomic sites which were previously documented as having no evidence of cutaneous disease on the whole body diagram; OR
- $\geq 25\%$  increase in the number of raised lesions (minimum of 5 raised lesions if there are very few raised lesions, for example  $<8$ ) whichever is greater. Photographic documentation of “gross” or significant progression, particularly in areas that were not being followed, will be of particular value.

In order to classify a response as PR, the subject must have at least a PR in either the cutaneous or noncutaneous sites of disease and no evidence of progression as defined in the above criteria. In order to classify a response as a CR, the subject must have a CR in both the cutaneous (if applicable) and noncutaneous (if applicable) sites of disease and no evidence of progression as defined by the above criteria.

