### **3.0 PATIENT SELECTION**

#### **3.1 Inclusion Criteria**

Subjects must meet all of the following conditions to be eligible for enrollment into the study:

- 3.1.1 Biopsy-proven KS involving the skin, with or without lymph node, oral cavity, gastrointestinal (GI) tract and/or lung involvement. GI and pulmonary involvement must be asymptomatic or minimally symptomatic and not require systemic cytotoxic chemotherapy. At least five measurable, previously non-radiated, cutaneous lesions must be present, which can be used as indicator lesions. Additionally, patients will need a sufficient number of non-indicator cutaneous lesions measuring  $\geq 4 \times 4$  mm to obtain a total of four (4) 3-mm punch biopsies, two at baseline and two during the course of treatment.
- 3.1.2 Serologic documentation of HIV infection at any time prior to study entry, as evidenced by positive ELISA, positive Western Blot, or other federally approved licensed HIV test, or a detectable blood level of HIV RNA.
- 3.1.3 Karnofsky performance status  $\geq 60$ .
- 3.1.4 The following laboratory parameters within 21 days prior to enrollment:
  - 3.1.4.1 Hemoglobin  $\geq 8$  g/dL.
  - 3.1.4.2 Absolute neutrophil count  $\geq 1,000$  cells/mm^3.
  - 3.1.4.3 Platelet count  $\geq 75,000$ /mm^3.
  - 3.1.4.4 Creatinine  $\leq 2.0$  mg/dL.
  - 3.1.4.5 Bilirubin values:
    - For patients who are not receiving indinavir or atazanavir, total serum bilirubin should be Grade 0 ( $\leq$  upper limit of normal [ULN]).
    - For patients who are receiving indinavir or atazanavir, there is no specific limit on total serum bilirubin, but direct serum bilirubin should be  $\leq 30\%$  of the total bilirubin.
  - 3.1.4.6 AST (SGOT) and ALT (SGPT)  $\leq$  Grade 1 (2.5 x ULN).
  - 3.1.4.7 INR and aPTT  $\leq$ ULN.
  - 3.1.4.8  $< 2+$  proteinuria.
- 3.1.5 Life expectancy  $\geq 3$  months.

- 3.1.6 Age  $\geq$  18 years.
- 3.1.7 Ability and willingness to give written informed consent.
- 3.1.8 Women of child-bearing potential must have a negative pregnancy test within 72 hours before initiation of study drug dosing. Post menopausal women must be amenorrheic for at least 12 months to be considered of non-childbearing potential.

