- Identify marker lesions: Select five bi-dimensionally measurable marker lesions for assessing changes in lesion dimension. Select the largest lesions with clearly defined margins. Marker lesions will be photographed to document lesion appearance and affected areas at baseline, in accordance with the guidelines for photography in Appendix XIV. Additionally, patients will need a sufficient number of non-indicator cutaneous lesions measuring  $\geq 4 \times 4$  mm to obtain a total of four (4) 3-mm punch biopsies, two at baseline and two during the course of treatment.
- For subjects with  $< 50$  total skin and oral lesions, all lesions must be evaluated for changes in number and characteristics. For subjects with  $\geq 50$  total skin and oral lesions, choose up to three representative areas for evaluating change in lesion numbers and characteristics (preferably an area with  $\geq 5$  lesions), with a total of at least 20 lesions.

NOTE: A representative area is a single extremity, the back, chest, or face that has lesions similar in characteristics, i.e., nodularity, size, color, and number, to those found on other parts of the body. A representative area does not need to be the area with the largest number of lesions but should contain lesions that are truly representative of those throughout the remainder of the body.

4.1.8 Staging Criteria (to be done within 28 days prior to study enrollment). KS staging will be based on the modified AIDS Clinical Trials Group (ACTG) Oncology Committee Staging Criteria (see Appendix III).

4.1.9 If specific consent obtained (see Appendix VIII), specimens for the AIDS and Cancer Specimen Resource (ACSR) will be collected within 28 days prior to enrollment (see Appendix VII for specimen handling).

4.1.10 KSHV viral load (see Appendix VI).

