#### 4.2.2 Biologic Endpoints

4.2.2.1 A 3-mm punch biopsy of a non-indicator KS lesion will be performed at baseline and between Days 22 and 28 of cycle 1. Biopsies will be fixed in formalin and studied by immunohistochemistry (IHC) for expression of the following: VEGF, VEGFR-2, VEGFR-3, phospho-Akt, KSHV LANA, orf59, p53 and HIF-1 $\alpha$ . Tumor cell proliferation will be assessed by Ki-67 staining. Change in the intensity or distribution of a particular marker will be evaluated. Ki 67 staining will be quantified as a percentage of tumor cells. All other immunohistochemical staining will be described with a score (0, 1+, 2+) and a description of the distribution of the signal (endothelial cells, spindle cells, infiltrating lymphocytes, etc.). Depending on the results of these assays, other potential immunohistochemical markers characteristic for KS may also be measured. A detailed protocol is provided in Appendix XIII.

Evaluation by IHC of the effects of PTC299 on KSHV LANA and orf 59 is based on the hypothesis that either VEGF depletion directly, or VEGF inhibition-induced hypoxia indirectly, may induce KSHV lytic gene expression. Because reduction of VEGF production is expected to reduce capillary-dependent oxygen flow to the tumor, this will, in turn, induce hypoxia. Hypoxia causes p53-dependent apoptosis but also, via HIF-1 $\alpha$ , induces VEGF. HIF-1 $\alpha$  and the cellular response to hypoxia are modulated by KSHV. Hence, p53, HIF-1 $\alpha$ , and some of their representative targets will be characterized by IHC as secondary biological endpoints.

4.2.2.2 A separate 3-mm biopsy of a non-indicator KS lesion will be performed at baseline and again between Days 22 and 28 of cycle 1 to assess viral gene expression within tumor at the messenger RNA level. Real-time QPCR based profiling of KSHV transcription will be used to test the hypothesis that depletion of VEGF directly or indirectly through the induction of hypoxia may lead to changes in KSHV transcription. This has previously been observed in laboratory studies.[134-137] A detailed protocol is provided in Appendix V.

4.2.2.3 Using the same biopsies as described in Section 4.2.2.2, Real-time QPCR based profiling will be used to test the hypothesis that depletion of VEGF directly, or indirectly through the induction of hypoxia, may lead to changes in cellular gene transcription.

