Reverse-transcription (RT) coupled to amplification using polymerase chain reaction (PCR) is widely recognized as the most sensitive method to detect the presence of specific RNAs. We will use real-time quantitative RT-PCR. This assay measures the amount of PCR product based on hybridization to a sequence-specific dual-labeled fluorogenic oligonucleotide (Taqman™) or intercalation of a fluorescent dye. Fluorescence is recorded at each cycle. So-called Ct-values indicate the cycle at which the fluorescence crosses a particular threshold (3 times standard deviation (SD) of the non-template control (NTC)). Hence, Ct-values indicate the abundance of a given mRNA on a log scale. A low Ct value represents a highly abundant target mRNA (Heid, Genome Res. 6:968-94,1996).

Specifically, we will use biopsies of Kaposi's sarcoma preserved in RNAlater (Ambion) at baseline and at indicated intervals after treatment. Total RNA will be isolated using RNeasy (Qiagen, Crawfordsville, IN) according to the supplier's protocol and reverse-transcribed using Mo-MuLV reverse transcriptase and 120 pmol random hexanucleotide primers (Taqman™MRT, Applied Biosystems Inc., Foster City, CA). After incubation at 42°C for 35 min, the reaction is stopped by heating to 95°C for 5 min, the cDNA pool is diluted, and the resulting sample analyzed by real-time quantitative PCR using a dedicated Roche LC480 machine and universal cycle conditions. We will use commercial SYBR-green-based PCR (Roche Inc., Indianapolis, IN) as a uniform detection method.

Biopsies should be obtained by standard punch technique, using a THREE (3) mm punch. Tumor biopsies should be completely within the margins of the lesions. A second biopsy should be obtained at baseline only from adjacent normal skin.

Each specimen should then be immersed in 1.5 ml RNAlater (Ambion Inc. cat#AM7022) and stored at FOUR (4) °C until shipment and labeled as follows:

Samples must be labeled with the bar-coded labels provided. Each sample should be labeled with the following information:

- **Protocol #:** “AMC-059”
- **Nine (9) Digit Subject ID:** “XXX-XXX-XXX”
- **Date Sample Collection**
- **Specimen Type** “KS tumor” or “normal skin”
- **Specimen Purpose:** “RNA levels”

**Supplies:** AMC sites will be provided five pre-filled vials of RNAlater and supplies will be replenished upon request to the [name] Laboratory.

The samples should be shipped by overnight courier on wet ice within 2 weeks to:

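### The partial-response criteria do not say how lesions biopsied under the protocol are scored, so a healed biopsy site read as gone or flat counts toward response

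*Combined protocol and SAP*

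**What the plan says.** Section 3.1.1 requires five measurable indicator lesions ("At least five measurable, previously non-radiated, cutaneous lesions must be present, which can be used as indicator lesions") and enough further non-indicator lesions of at least 4 x 4 mm "to obtain a total of four (4) 3-mm punch biopsies, two at baseline and two during the course of treatment". Section 4.2.2.1 sets the immunohistochemistry pair: "A 3-mm punch biopsy of a non-indicator KS lesion will be performed at baseline and between Days 22 and 28 of cycle 1". Section 4.2.2.2 adds the RNA pair: "A separate 3-mm biopsy of a non-indicator KS lesion will be performed at baseline and again between Days 22 and 28 of cycle 1". Appendices V and XIII both set the technique: "Tumor biopsies should be completely within the margins of the lesions".

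For subjects with fewer than 50 lesions, section 4.1.7 says that "all lesions must be evaluated for changes in number and characteristics". For subjects with 50 or more, up to three representative areas are followed, "with a total of at least 20 lesions".

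Section 8.1.2 gives three alternative routes to partial response (PR), provided that there are no new lesions:
- a fall in lesion count: "A 50% or greater decrease in the number of all previously existing lesions lasting for at least 4 weeks";
- complete flattening of at least half of all raised lesions;
- a 50% fall in the summed products of the marker-lesion diameters.

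The first response assessment is at Day 29 (section 8.0). The baseline tumour assessment may be made up to 14 days before treatment (section 4.1.7). Sections 3.1.1, 4.1.7, 4.2.2, 8.1 and 11.2 and Appendices V, XIII and XIV do not exclude biopsied lesions from the counts, say how a biopsied site is scored, or order the baseline count against the baseline biopsies.

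**The concern.** Confining biopsies to non-indicator lesions protects only the marker-lesion route. The other two routes count lesions that the protocol itself has altered. The on-treatment punches always come after the baseline count and within about a week of the Day 29 assessment; a footnote to Appendix I allows them on Day 29 itself, before dosing. The baseline punches may also follow the count, since no order is set.

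If a biopsied site is scored as a lost lesion, or as a raised lesion that has become flat, the subject moves toward PR for a reason unrelated to the drug. Where biopsy changes these scores in that way, the shift favours response, and it can also offset a rise in the counts used for progression. Response rate (CR + PR) is a primary objective, tested in a single arm against 10% in section 11.1, so no control group would cancel the shift. Subjects with few lesions are the most exposed.

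**Working it through.** **The plan's own figures.** Section 11.1 gives 0.697 as the probability of stopping with at most 1 response in 11 at a true rate of 10%. The exact binomial gives 0.6974. It also says that 4 or more responses in 12 has probability below 5% at 10%; the exact value is 0.0256. Both reproduce. The documents give no figure for biopsied lesions.

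**How much of a lesion a punch takes.** Punch area is π × 1.5² = 7.07 mm². A 4-mm round lesion has area π × 2² = 12.57 mm², so 1 − 7.07/12.57 = 44% remains. A 4 x 4 mm square has 16 mm², so 56% remains. Larger lesions keep more.

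**Count route.** Let N be the number of lesions counted and b the number of biopsied lesions scored as gone. PR needs ceil(N/2) lesions gone.
- As written, the other lesions that must clear number ceil(N/2) − b, out of N − b.
- With biopsied lesions excluded from numerator and denominator, ceil((N − b)/2) must clear, out of N − b.

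With five indicator lesions and four separately biopsied ones, N is at least 9, so the biopsied share is at most 4/9 = 44.4%. For two biopsied lesions it is at most 2/7 = 28.6%. Neither reaches 50%. With 50 or more lesions and the minimum of 20 counted, the share is at most 4/20 = 20%.

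For illustration, assume that each untouched lesion independently reads as gone with probability 0.20 and that all b biopsied sites read as gone. Neither assumption comes from the documents. The probabilities are binomial upper tails, P(X ≥ number needed).

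| N | b | As written: needed | Probability | Excluded: needed | Probability |
|---|---|---|---|---|---|
| 9 | 4 | 1 of 5 | 0.67 | 3 of 5 | 0.058 |
| 12 | 4 | 2 of 8 | 0.50 | 4 of 8 | 0.056 |
| 20 | 4 | 6 of 16 | 0.08 | 8 of 16 | 0.007 |
| 9 | 2 | 3 of 7 | 0.148 | 4 of 7 | 0.033 |
| 12 | 2 | 4 of 10 | 0.121 | 5 of 10 | 0.033 |
| 20 | 2 | 8 of 18 | 0.016 | 9 of 18 | 0.004 |

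At N = 49 with b = 4, the requirement is 21 of 45 as written and 23 of 45 with exclusion. Both probabilities are below 0.001.

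**Flattening route.** Let R be the number of raised lesions at baseline. If b biopsied raised lesions are scored as macules, biopsy alone meets the criterion when b/R ≥ 0.5, that is R ≤ 2b: R ≤ 8 for b = 4 and R ≤ 4 for b = 2. As written, the 4-week duration is attached only to the count route.

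**Effect on the decision rules.** Suppose that a fraction f of true non-responders is scored PR in this way (an assumption). A true rate of 10% is then observed as 0.10 + 0.90f.

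| f | Observed rate | P(stop at 11) | P(≥ 4 of 12) |
|---|---|---|---|
| 0 | 10.0% | 0.697 | 0.026 |
| 2% | 11.8% | 0.621 | 0.044 |
| 5% | 14.5% | 0.511 | 0.083 |
| 10% | 19.0% | 0.353 | 0.180 |

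**The case against.** The strongest reply is that the protocol samples lesions and does not remove them. The punch must lie inside the lesion margins, and roughly half of even the smallest permitted lesion is left. A residual lesion still counts as one lesion, and a raised rim outside the punch would defeat complete flattening. If sites persist as lesions, there is no bias. If the baseline count follows the baseline punches, those two lesions need add none. All of this stands. A reader might infer that lesions are punched out and lost for good; the documents do not support that. They are silent on healing and on how a site is scored, and that silence is the point.

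The larger figures also stack unfavourable conditions: four different lesions, baseline punches after the count, every site read as gone, and few lesions. The documents do not say that the four punches come from four different lesions, so nine is not established as the smallest eligible lesion count. This stands too, and is why the two-lesion rows are shown.

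A reader might compare 0.67 with the 0.02 that applies to nine lesions with no biopsy effect (5 of 9 needed). That comparator keeps the biopsied lesions in the denominator and does not match the remedy; the matching figure is 0.058.

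Finally, the baseline and change-of-category photographs and the whole-body diagram could help to check biopsy sites. They are useful records, but no rule tells the assessor to use them for this purpose.

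**Conclusion.** The gap is real: the criteria count all lesions, the protocol alters up to four of them, and no scoring rule covers the result. A healed site read as gone or flat moves a subject toward PR. On the count route, biopsy can only reduce the number of other lesions that must clear; on the flattening route, it could suffice alone in subjects with few raised lesions. The effect is substantial at 9 to 12 lesions under the stated assumptions, small at 20 if two lesions are affected, and negligible near 49.

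The realised bias cannot be estimated, because the documents give neither the distribution of lesion counts nor how often a biopsied site is scored as gone or flat. A reader might infer that the response rate is materially inflated or that the sample size is wrong. Neither follows, and no sample-size figure changes. This is an inexpensive improvement to the endpoint definition, not an error that invalidates the design.

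**What to change.** In sections 4.1.7 and 8.1:
- Identify each biopsied lesion on the body diagram and the lesion form.
- Exclude it from numerator and denominator of the total-lesion and raised-lesion counts, for both PR and progression. Keep it in the assessment of complete response, which requires no detectable residual disease anywhere.
- Take the baseline count so that the lesions biopsied at baseline are already identified.
- In subjects with 50 or more lesions, biopsy outside the representative areas where possible.

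For subjects already treated, repeat the count and flattening routes without the biopsied lesions as a sensitivity analysis, where records identify them. The documents do not show that such records exist for every subject.

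The cost is a few sentences and a flag on the lesion form, with no extra procedure. Slightly fewer lesions are counted, and the response rate may be slightly lower.

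### Section 8.1.2 puts the 4-week duration on only one of three routes to partial response, so a single monthly reading on the flattening or marker-area route counts, and the response rate can sit above the durable rate by an amount the documents do not give.

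*Combined protocol and SAP*

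**What the plan says.** Section 8.1.2 first requires that there be no new lesions, no new visceral sites, and no new or worse edema or effusion. It then joins three routes by OR:

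- Lesion count: "A 50% or greater decrease in the number of all previously existing lesions lasting for at least 4 weeks".
- Flattening: "Complete flattening of at least 50% of all previously raised lesions".
- Marker area: "A 50% decrease in the sum of the products of the largest perpendicular diameters of the marker lesions".

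Only the first carries a duration. CR in Section 8.1.1 also carries one: "absence of any detectable residual disease, including tumor-associated edema, persisting for at least 4 weeks".

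The schedule in Section 8.0 is monthly, with a window of 7 days either way: "All subjects will be evaluated for response by physical examination and by relevant imaging studies at Day 29 and every 28 days thereafter". The overall classification rule for PR adds only that "the subject must have at least a PR in either the cutaneous or noncutaneous sites of disease and no evidence of progression". Section 7.0 mentions confirmation for CR alone. Sections 8.1.6 and 8.1.8 date response from its first documentation. Section 11.2 analyses CR + PR as Section 8.0 defines it, with no confirmation step.

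**The concern.** Response rate is one of three primary objectives (Section 2.1.3) and is the one tested in the Phase 2 portion. Section 11.1 bases three rules on it: continue with at least 2 responders of 11, reject the 10% null with at least 6 in total, and infer a rate above 10% with at least 4 of 12.

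The trial is open-label and single-arm, and no independent response reading is specified. A subject who never does better than stable disease has about six monthly readings before removal under Section 7.0. On two of the three routes any one of those readings is enough. Flattening is a visual judgement, and the PR definition sets no minimum number of raised lesions. The progression rules in Section 8.1.4 do set a floor of five when raised lesions are few.

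The result is one endpoint that mixes durable and possibly momentary responses. If the authors meant 4 weeks to apply throughout, the text does not say so, and sites may apply it differently.

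**Working it through.** **Text.** Side by side, CR and the count route need 4 weeks; the flattening and area routes do not. Sections 7.0, 8.1.6 to 8.1.8, 11.1 and 11.2 and the overall classification rule add neither duration nor confirmation for PR. For the same subjects, a count that accepts single readings can only equal or exceed a count that requires a second one. The direction follows from the wording alone.

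**The plan's own figures** (Section 11.1 unless stated):

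- Stopping at a 10% rate: 0.9^11 + 11 × 0.1 × 0.9^10 = 0.3138 + 0.3835 = 0.697, as stated.
- Stopping at a 35% rate: 0.0088 + 0.0518 = 0.061, against a stated 0.059. The gap is immaterial here.
- P(at least 4 of 12) at 10%: 0.026, consistent with the stated figure of below 5%.
- Section 11.2 half-width: 1.96 × √(0.25/12) = 28.3%, as stated.

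**Two-stage rule.** N = 11 + 18 = 29 to 11 + 21 = 32. With X1 the responders among the first 11 and X2 those among the rest,

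R(p) = Σ(k = 2 to 11) P(X1 = k) × P(X2 ≥ 6 − k).

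At p = 0.10, R is 0.051 for N=29 and 0.070 for N=32. The excess over 0.05 comes from the sample-size rule, not from PR duration.

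**Illustration.** Assumptions, none of them from the documents except the look count: the true durable rate is 10%; each non-responder has six looks; each look has an independent chance q of a transient PR reading. Then

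p = 0.10 + 0.90 × [1 − (1 − q)^6].

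| q per look | Apparent rate | R, N=29 | R, N=32 | At least 4 of 12 |
|---|---|---|---|---|
| 0 | 10.0% | 0.051 | 0.070 | 0.026 |
| 0.1% | 10.5% | 0.063 | 0.085 | 0.03 |
| 0.5% | 12.7% | 0.124 | 0.161 | 0.055 |
| 1% | 15.3% | 0.228 | 0.281 | 0.097 |
| 2% | 20.3% | 0.472 | 0.535 | 0.213 |

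Example at q = 1%: 1 − 0.99^6 = 0.0585, and 0.10 + 0.90 × 0.0585 = 0.153.

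Six looks is about the most a non-responder has, because progression ends treatment sooner. With three looks and q = 1%, R is 0.12 (N=29) and 0.16 (N=32).

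**With a second consecutive reading required.** At q = 2% the chance of two consecutive transient readings in six is 0.002, so p = 0.10 + 0.90 × 0.002 = 0.102. Over the table's range R is 0.051 to 0.055 (N=29) and 0.070 to 0.075 (N=32), and the 4-of-12 probability is 0.026 to 0.027.

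**Limit of confirmation.** Suppose every subject had two raised lesions and each were misread as flat with probability 5% (assumed). A spurious PR at one visit then has probability 1 − 0.95² = 9.8%. Two in a row within six visits has probability 4.4%, so p = 0.10 + 0.90 × 0.044 = 13.9% and R is 0.17 to 0.22 even with confirmation.

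**Visit window.** Under Section 8.0, consecutive visits can be 28 − 7 − 7 = 14 days apart. Under the 3-day window in Section 4.2 they can be 28 − 3 − 3 = 22 days apart. The next scheduled visit therefore does not guarantee 4 weeks.

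**The case against.** The strongest reply is that inflation is not shown. The documents give no rate of transient readings, and they do not say whether the 10% benchmark is a confirmed rate. If it rests on the same definition, accepting single readings does not raise type I error against it. This stands: the table illustrates sensitivity and does not estimate the trial's error rate.

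There are also safeguards. PR is barred by new lesions, new or worse edema, or progression. Photographs are required when the response category changes. The area route uses five measurable lesions with clear margins and a 50% threshold. These lower the chance of a spurious call, particularly on the area route, but none requires a second reading.

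A reader might infer that the note in Section 8.1.4 on variable lesion appearance concedes the problem. It does not. It sits under progression, takes foot lesions (flat ones especially) as its example, and warns of new lesions being counted in error. That error would block a PR, not create one.

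A reader might also infer that confirmation cures the endpoint. It removes transient errors only. A lesion misread the same way twice survives it, and so does the problem of very few raised lesions.

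**Conclusion.** The gap in the text is real: two of three PR routes need no duration, and nothing elsewhere supplies it. The response rate, and the three rules that use it, can therefore be biased upward relative to a durable-response rate.

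The size is unknown. Under the stated assumptions it runs from slight at q = 0.1% to large at q = 2%, where rejection is 0.47 to 0.54. Those figures depend on independent errors, six looks, and a 10% rate that means durable response. The documents support the statement that the endpoint can be inflated; they do not support the statement that it is, or by how much. This is a cheap improvement to a primary endpoint that should be made.

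**What to change.** - Move the 4-week duration to the head of Section 8.1.2 so that it governs all three PR routes. State that it is met by a second qualifying assessment at least 28 days after the first; the interval must be explicit because of the visit window.
- Carry the same definition into Section 11.2 as the primary CR + PR count, and say that the Section 11.1 rules use it.
- Apply it to all subjects, including the 9 + 8 = 17 already enrolled in Stages 1 and 2, from their recorded monthly assessments. This avoids mixing definitions, including in the count of 11.
- Report unconfirmed PRs separately as a sensitivity analysis.

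**Cost.** No planned procedure is added, since assessments are already monthly. A response first seen at the last assessment may stay unconfirmed, so the rate may be slightly lower. The tumor assessment 30 days after discontinuation (Section 4.4) could be considered for such cases. Earlier records need re-reading. Section 7.0 uses the same response categories at six cycles, so the sponsor must reconcile it with the revised definition; I propose no treatment rule. The change does not deal with persistent misreads or with subjects who have very few raised lesions.
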